undergo a pregnancy test and will be informed that they should not plan to become pregnant whilst participating in the study.

TREATMENT	Participants in the Intervention groups will receive enteric coated capsules containing sodium propionate. Participants in the Control group will receive sodium chloride in the same capsule formulation. For each study one dose per visit will be taken.
DURATION	
Study 1: Individuals participating in the dose ranging study will be asked to attend our clinical trials unit on a single day for a total of 8 hours. Volunteers taking part in the full pharmacokinetic study will be asked to attend the clinical trials unit twice for a total of 8h at each visit.
 
Study 2: Individuals will be asked to attend the clinical trials unit on 5 separate occasions each visit lasting 4 hours during which oral glucose tolerance testing will take place.
 
Study 3: All participants will be asked to attend the clinical trials unit to undertake an oral glucose tolerance test in order to screen for impaired glucose tolerance. Individuals will be asked to attend the clinical trials unit on two separate occasions each visit lasting 4 hours for the main part of the study.

MEASURES	
Study 1: The primary outcome will be peak plasma concentration of propionate coupled with determination of the elimination profile. Secondary outcomes will aim to understand the acute effects of propionate and will include plasma insulin, glucagon like peptide-1 (GLP-1), peptide yy (PYY), leptin, glucose and free fatty acid concentrations following propionate administration.
 
Study 2: Our primary outcome will be the insulinogenic index which is the increase in plasma insulin from 0-30mins during an oral glucose tolerance test. Secondary outcomes will be plasma concentrations of insulin, Glp-1, free fatty acids, PYY, leptin, glucose and free fatty acids will be measured during the oral glucose tolerance test.
 
Study 3: The primary outcome will be measurement of beta cell function as determined by the calculation of acute insulin response to glucose (the incremental area under the insulin profile from 0-10minutes following an intravenous glucose bolus) during an intravenous tolerance test.
 
Secondary outcomes will be plasma concentrations of insulin, GLP-1, PYY, Leptin glucose and free fatty acids.

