Study Day1: Using the data from the dose ranging study a full pharmacokinetic study will be undertaken. Participants will arrive at the St. John McMichael Centre (Hammersmith

hospital) having fasted from the previous evening and a canulae will be inserted into a peripheral vein. Blood samples (10ml) will be taken at -10 and 0 post oral propionate administration (3g) then 4 samples will be taken during each of the absorption and early elimination phases, followed by further samples post peak for a total of 6 samples in this phase, over three half-lives. In total 120mls of blood will be drawn.

Study Day 2: At least a week following the first study day participants will be asked to attend a repeat visit at the St John Mc Michael Centre which will follow the same protocol as for study day 1 but participants will be given a 6g dose of propionate.

Blood samples will be analysed using the following methods:

- Propionate by Mass spectrometry
- Insulin, GLP-1, PYY, leptin and non-esterified fatty acids will be measured using commercially available kits.
- Glucose will be measured using a glucometer.

Study 2

Aim: To dose dependently determine if propionate augments beta cell function.

Study methodology: Participants will undergo a series of oral glucose tolerance tests (OGTT) following administration of propionate. Each participant will receive all doses of propionate and each study day will be separated by at least 1 week.

Participants: 30 healthy men and women aged 18-70, body mass index (BMI) 20-25 kg/m², with normal fasting glucose and HbA1C.

Support for number of participants: A previous small study of the effects of propionate on glucose levels in humans identified a 47.4% reduction in glucose AUC over 2 hours following consumption of a standard 50 g carbohydrate load supplemented with propionate. Mean OGTT glucose AUC in a group of 514 healthy subjects was 40.8 mmol.min (SD 7.1 – unpublished data from the study described in Diabetic Medicine 2007;24:1269-1278). A 47.4% reduction in OGTT glucose AUC would result in a mean glucose AUC of 21.5. Using data from the same study, a mean insulinogenic index of 0.99 (SD 0.85) was observed, regression analysis estimated that a 47.4% reduction in glucose AUC would be associated with an increase in insulinogenic index of 0.73 SD. This can be detected as significant at p<0.05, with 80% power using 30 in each group. Screen failures will be replaced.

Health Screening and enrolment Visit

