Participants will arrive fasted from 8pm the previous evening. They will be clerked and examined by a research doctor. Measurements of height, weight, body fat content, blood pressure , an ECG and a blood test (for full blood count, urea and electrolytes, liver function tests, lipid profile, fasting glucose, HbA1C) will be taken. Screen failures will be replaced.

Study Day 1-5 Participants will undergo a frequently sampled oral glucose tolerance test (OGTT) to detect changes in insulin sensitivity and beta cell function. Participants will be asked to refrain from strenuous exercise and alcohol on the day prior to each study. They will be asked to eat a standard meal of your choice before the study (e.g. ready-made meal) and then be required to fast overnight.

They will be asked to come to the Clinical Investigations Unit at Hammersmith Hospital at 8:30am, having fasted from 8pm the previous day. A small plastic tube (cannula) will be inserted into their arm and a blood sample taken. This will be in place for the duration of the study day. Baseline blood samples will be taken at -30 and -10mins before the participant will take capsules containing either sodium chloride (placebo control) or sodium propionate. They will then consume a 250 ml drink containing 75 g of glucose at a pre-determined time so that the expected peak blood glucose level coincides with the expected peak propionate blood concentration. During the next 3 hours they will have blood samples taken at 0, 10, 20, 30, 60, 90, 120, 180 mins after the glucose drink. A total of 90 ml of blood will be taken (about 6-8 tablespoons of blood). These will be taken through the cannula. After 3 hours the cannula will be removed and the participant will be provided with a light snack and able to go home.

Participants will be asked to attend four repeat visits with a minimum of a week between visits. They will randomly be assigned an oral dose of propionate, either 0, 1, 3, 6, 9g.

Blood samples will be analysed using the following methods:

- Propionate by Mass spectrometry
- Insulin, GLP-1, PYY, leptin and non-esterified fatty acids will be measured using commercially available kits.
- Glucose will be measured using a glucometer.

Study 3

Aim: To determine the effect of propionate on beta cell function using the gold standard intravenous glucose tolerance (IVGTT) test in healthy participants and healthy volunteers at risk of developing diabetes.

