7. STATISTICS AND DATA ANALYSIS

An independent researcher (i.e. not linked to the study) will be given the task of randomisation, which will be by sealed envelopes.

Although the data handling and statistical methodology can only be confirmed once all the data is collected. Our intention is to use parametric techniques to analyse the data if it is normally distributed. We will therefore use T-tests for comparisons between two groups and ANOVA for comparisons of three or more groups.

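### Study 2 draws two pre-capsule samples at each of five visits but gives them no role; pre-specify a within-participant crossover model with the visit's pre-capsule mean as a covariate, for a gain that the documents cannot quantify.

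*Combined protocol and SAP*

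**What the plan says.** - **Samples.** Section 3 (Study 2, Study Day 1-5): "Baseline blood samples will be taken at -30 and -10mins before the participant will take capsules". With five visits, that is 2 × 5 = 10 pre-capsule samples per participant.
- **Time 0.** In the same paragraph the glucose drink follows the capsules, timed so that the expected glucose and propionate peaks coincide. Eight samples from 0 to 180 min are counted from the drink, so the 0 min sample is taken after dosing.
- **Outcomes.** Section 1 (Measures, Study 2): "Our primary outcome will be the insulinogenic index which is the increase in plasma insulin from 0-30mins during an oral glucose tolerance test". The secondary outcomes are concentrations of insulin, gut hormones, leptin, glucose and free fatty acids during the test, with no summary measure named.
- **Design.** Section 3 (Study 2): "Each participant will receive all doses of propionate and each study day will be separated by at least 1 week". The doses are 0, 1, 3, 6 and 9 g.
- **Analysis.** Section 7: "We will therefore use T-tests for comparisons between two groups and ANOVA for comparisons of three or more groups". No participant term, period term or covariate is named, and the section leaves the methods to be settled after data collection.

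No section says how the -30 and -10 min samples enter an outcome or an analysis.

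**The concern.** Visits are at least a week apart, and a person's fasting state can differ from one visit to the next. A within-participant analysis removes stable differences between people but not this visit-to-visit variation. A value measured before dosing at the same visit can remove whatever part of it predicts the outcome. The 0 min sample is a poor substitute because it may already carry a propionate effect.

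Two things are at stake. The first is precision in comparing doses: Study 3 takes forward the dose that Study 2 finds most effective, and differences between active doses may be smaller than the effect used for sizing. The second is analytic freedom. Ignoring, subtracting or adjusting for the pre-capsule value gives estimates of quite different precision, and section 7 leaves that choice open until the data are in.

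**Working it through.** **1. The plan's own figure.** Section 3 gives "a mean insulinogenic index of 0.99 (SD 0.85) was observed" and assumes an "increase in insulinogenic index of 0.73 SD", which is 0.73 × 0.85 = 0.62 index units. It concludes: "This can be detected as significant at p<0.05, with 80% power using 30 in each group". Taking the test as two-sided (not stated), n = 2(1.960 + 0.842)² / 0.73² = 29.5, so 30 per group. Power at 30 is 80.7% by the normal formula and 79.4% by the t distribution. The figure reproduces, but as a comparison of two independent groups with no baseline term.

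**2. What the crossover already removes.** With total SD set to 1 and between-visit correlation r (assumed), a within-participant dose contrast has variance 2(1 - r)/30. Residual degrees of freedom are 150 observations - 30 participants - 4 periods - 4 doses = 112. Unadjusted power at 0.73 SD is 80%, 92%, 98% and over 99% for r = 0, 0.3, 0.5 and 0.7.

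**3. What the pre-capsule value can add.** Let ρ be the within-person, visit-to-visit correlation between pre-capsule value and outcome. The documents give no ρ, so a range is assumed.

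- As a covariate, contrast variance is multiplied by about (1 - ρ²) × 111/110. The last factor is the price of one degree of freedom.
- Subtracted, it is multiplied by 1 + λ² - 2ρλ, where λ is the ratio of baseline SD to outcome SD. At λ = 1 this is 2(1 - ρ). Subtraction helps only when ρ exceeds λ/2.

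The check was a simulation of 30 participants and five periods, with cyclic dose sequences, λ = 1, no carry-over and 1,500 replicates per ρ:

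| ρ | Covariate, formula | Covariate, simulated | Subtracted, simulated | Contrasts with wider estimated SE after covariate |
|---|---|---|---|---|
| 0 | 1.01 | 1.01 | 2.01 | 82% |
| 0.1 | 1.00 | 0.99 | 1.81 | 59% |
| 0.2 | 0.97 | 0.97 | 1.62 | 24% |
| 0.3 | 0.92 | 0.92 | 1.43 | 5% |
| 0.5 | 0.76 | 0.77 | 1.05 | 0% |

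In participants, ρ = 0.3 is worth 30/0.92 = 32.6, or about 33 instead of 30. ρ = 0.5 is worth 30/0.772 = 38.9, or about 39.

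**4. In power, with r = 0.5 assumed.** At 0.73 SD, power is 97.7% unadjusted, 98.6% with the covariate at ρ = 0.3, and 91.8% with subtraction at ρ = 0.3 and λ = 1. For a smaller difference of 0.4 SD, power is 58.4% unadjusted, 62.4% with the covariate at ρ = 0.3 and 70.8% at ρ = 0.5.

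**5. Primary against secondary outcomes.** Suppose fasting insulin at one visit is shifted by δ and the whole profile moves with it. The primary outcome becomes (I30 + δ) - (I0 + δ) = I30 - I0, so the shift cancels. In a total AUC from 0 to 180 min the same shift adds 180δ. The covariate therefore has more to explain in the secondary concentrations. For the primary outcome it can help only with non-additive effects, for example if the insulin response scales with the fasting level.

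**The case against.** The strongest case against is that this is an optional refinement of unknown value. The primary outcome is already an increment, the design already makes each person their own control, and section 3 standardises conditions with an evening fast, a fixed morning start and limits on alcohol and exercise. Fasting drift may be small, and ρ may be near zero. At the planned effect, with r = 0.5, the covariate adds less than one point of power at ρ = 0.3. ANOVA could also be run in a repeated-measures form, and no stated result becomes invalid without the covariate. All of this stands, and it limits the size of the point. It does not give the samples a role or fix the model in advance.

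Three stronger readings are tempting and not supported:

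- A reader might infer that adjustment would sharpen every dose contrast at no cost. It would not: at ρ = 0 the variance rises by about 1%, and at ρ = 0.1 the estimated SE is wider in more than half of contrasts.
- A reader might infer that adjustment cannot bias the comparison because that visit's dose cannot affect a pre-capsule value. This holds only if no earlier dose carries over into the later baseline. The documents give a minimum one-week gap but no evidence on carry-over.
- A reader might infer that raw secondary concentrations will be tested at every time point, with many false positives. No section proposes this, and a baseline covariate would not cure it.

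**Conclusion.** The point holds as a cheap improvement. The pre-capsule samples have no stated role, and the named tests do not reflect a five-period crossover. The documents do not establish how large the benefit is: over the assumed range of ρ from 0 to 0.5, contrast variance runs from about 1% worse to 23% better. The lower part of that range is plausible for the insulinogenic index; the raw secondary concentrations have more to gain. The finding against subtraction is firmer but conditional: with equal baseline and outcome variances it raises variance by about 43% at ρ = 0.3 and doubles it at ρ = 0. If the baseline SD is half the outcome SD (λ = 0.5), the factors are 0.95 and 1.25.

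These figures rest on a two-sided 5% test, 30 complete participants, dose orders balanced over periods, and no carry-over. All correlations are assumptions.

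**What to change.** Before analysis, write into section 7 for Study 2:

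1. A within-participant crossover model with participant, period and dose terms.
2. The mean of that visit's -30 and -10 min values as a covariate: fasting insulin, fasting glucose or both (chosen in advance) for the insulinogenic index, and the same analyte for each secondary outcome. Do not subtract the pre-capsule value.
3. Separation of within-person from between-person baseline variation, either with fixed participant effects or by adding each participant's mean baseline to a random-effects model.
4. One total AUC per visit for each secondary analyte. An incremental AUC would bring subtraction back.
5. The same model without the covariate as a sensitivity analysis, in case an earlier dose affects a later baseline.

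The cost is wording and one or two of the 112 residual degrees of freedom. No extra blood is drawn. The assay list in section 3 is not tied to time points, so the plan should also confirm that the pre-capsule samples are assayed for these analytes.

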Study methodology: Participants will undergo intravenous glucose tolerance tests. The effect of propionate on beta cell function will be determined in a randomised double blind placebo controlled crossover study.

Participants:

Cohort 1: 34 healthy men and women aged 30-70, body mass index (BMI) 25-35 kg/m², normal fasting blood glucose (below 5.5mmol/l and HbA1C less than 5.7% will be eligible to volunteer. Screen failures will be replaced.

Cohort 2: 34 men and women at risk of developing diabetes aged 30-70 with a body mass index (BMI) 25-35 kg/m² with fasting blood glucose between 5.6mmol/l and HbA1C between 5.8 and 6.5% will be eligible to volunteer. Screen failures will be replaced.

Support for number of participants: Our pilot data demonstrates mean Insulin AUC₁₀ of 8.1 for saline treated mice versus 11.3 for mice propionate-treated mice, an increase in the acute insulin response to glucose of 40%. Mean IVGTT-AIRg in a group of 306 healthy subjects was 492 mU.min (SD 48.7 - unpublished data from the study described in Diabetologia 2004;47:1157-1166). Using log-transformed data for IVGTT-AIRg, it was estimated that a 40% increase in IVGTT-AIRg would constitute an increase of 0.79 SD, which could be detected as significant at p<0.05, with 90% power using 34 in each group. Screen failures will be replaced.

Health Screening and enrolment Visit

Participants will arrive fasted from 8pm the previous evening. They will be clerked and examined by a research doctor. Measurements of height, weight, body fat content, blood pressure, an ECG and a blood test (for full blood count, urea and electrolytes, liver function tests, lipid profile, fasting glucose, HbA1C) will be taken. Screen failures will be replaced.

Visit 1: Oral glucose tolerance test.

The participant will be asked to come to the Clinical Investigations Unit at Hammersmith Hospital at 8:30am, having fasted from 8pm the previous day. A cannula will be inserted into a peripheral vein and two fasting blood samples taken at -30 and -10 mins before the participant consumes a drink containing 75 g of glucose. During the next 3 hours blood samples will be taken at 0, 10, 20, 30, 60, 90, 120, 180 minutes post glucose administration. A total of 100ml of blood will be taken.

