Visit 2 and 3: Participants will undergo a frequently sampled intravenous glucose tolerance test (IVGTT) to detect changes in insulin sensitivity and beta cell function. The day prior to the study subjects will be asked to refrain from alcohol and strenuous exercise and fast for 12 hours prior to the study. The study will be carried out at the St. John Mc Michael Centre (Hammersmith hospital). Subjects will have two cannulae placed in separate peripheral veins. Subjects will be given glucose (20% solution-0.3g/kg) directly into a peripheral vein following oral administration of propionate at the most effective dose determined in study 2. Timing of the glucose bolus will be determined from data gathered in study 1 and be given 5mins prior to the expected plasma peak concentrations of sodium propionate. Blood samples (10ml) will be taken at, -5, 0, 2, 4, 6, 8, 10, 19, 22, 30, 40, 50, 70, 100 & 180 where glucose is administered at time 0, in total 150ml of blood will be drawn. Participants will be administered human insulin (0.03units/kg, 'regular human insulin – Novo Nordisk') at 20 mins post glucose. Participants will be asked to attend a repeat visit with a minimum of a week between visits. Participants will be randomly assigned propionate or placebo.

Blood samples will be analysed using the following methods:

- Propionate by Mass spectrometry

- Insulin, GLP-1, PYY, leptin and non-esterified fatty acids will be measured using commercially available kits.
- Glucose will be measured using a glucometer.
-

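### Studies 2 and 3 are within-person crossovers, but the plan specifies neither the treatment sequences nor a period term, so chance order imbalance can cost precision that is almost free to keep

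*Combined protocol and SAP*

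**What the plan says.** Section 3 (Study Design) makes Study 2 a five-visit crossover: "Each participant will receive all doses of propionate and each study day will be separated by at least 1 week". The sample is stated as "Participants: 30 healthy men and women aged 18-70", and order is covered by one sentence, "They will randomly be assigned an oral dose of propionate, either 0, 1, 3, 6, 9g".

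Study 3 is a "randomised double blind placebo controlled crossover study" with 34 people in each of two cohorts and two test visits at least a week apart. Its order rule is "Participants will be randomly assigned propionate or placebo". Its dose is whichever proves most effective in Study 2.

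Section 7 (Statistics and Data Analysis) says that an independent researcher is "given the task of randomisation, which will be by sealed envelopes". It names t-tests for two groups and ANOVA for three or more, if the data are normal, and says that the methods can be confirmed only after data collection. Neither section mentions a sequence set, a Latin square, blocks, a ratio of first treatments, or participant or period as model terms.

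**The concern.** In a crossover, anything that changes across visits (familiarity with the test, assay batch, drift in the participant) cancels from a treatment contrast only if each treatment falls equally often at each visit or if the model removes the visit effect. The plan commits to neither. A plain paired t-test deals with differences between people but not with visit order.

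Two decisions rest on these contrasts. Study 2 selects the Study 3 dose from a single realised randomisation, so a dose that happens to fall at favourable visits gains a small advantage. Study 3 estimates the effect separately in healthy and at-risk cohorts. Different chance splits would leave different fractions of any visit effect in the two estimates, and the stated aims include the impact of diabetes risk.

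**Working it through.** **The plan's own sample sizes.** Two-sided 5% is assumed, because sidedness is not stated. With n per group = 2(z₁ + z₂)²/d²:
- Study 2: the plan says the glucose reduction "would be associated with an increase in insulinogenic index of 0.73 SD" and "This can be detected as significant at p<0.05, with 80% power using 30 in each group". 2 × (1.960 + 0.842)²/0.73² = 29.5, so 30.
- Study 3 (0.79 SD, 90% power): 2 × (1.960 + 1.282)²/0.79² = 33.7, so 34.

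Both reproduce, as comparisons of two independent groups. Neither calculation uses the within-person design or allows for visit order.

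**Study 3, if order is simply randomised.** The number starting on propionate is Binomial(34, 0.5).
- P(17:17) = 13.6%. P(20:14 or worse) = 39%. P(22:12 or worse) = 12%.
- P(at least one of two cohorts at 20:14 or worse) = 1 − (1 − 0.39)² = 63%.
- Share of the period effect left in an unadjusted paired contrast = |n₁ − n₂|/34. At 20:14 this is 6/34 = 0.18; at 22:12 it is 10/34 = 0.29. Over all splits the signed share has mean 0 and SD 1/√34 = 0.17.

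**Study 2, if each order is an independent random permutation.** Visit position has variance 2, and two doses in the same person have covariance −0.5. The difference in position therefore has variance 2 + 2 + 1 = 5. Over 30 people its mean has SD √(5/30) = 0.41 visits. In 20,000 simulated lists the absolute difference had 95th percentile 0.80 visits, and no list was exactly balanced.

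**Size on the outcome scale.** The documents give no visit effect, so these values are assumptions.
- Study 2, drift of 0.1 SD per visit: leakage has SD 0.1 × 0.41 = 0.04 SD, and is 0.08 SD at the 95th percentile, against a planned 0.73 SD.
- Study 3, period effect of 0.2 to 0.4 SD: a 20:14 split shifts the estimate by 0.18 × 0.2 = 0.035 to 0.18 × 0.4 = 0.07 SD, against a planned 0.79 SD.
- Study 3, SD of the unadjusted estimate relative to no period effect = √[(2(1 − ρ) + π²)/(2(1 − ρ))]. With ρ = 0.5 and π = 0.2: √(1.04/1.00) = 1.02. With ρ = 0.7 and π = 0.4: √(0.76/0.60) = 1.13.
- Type I error of the unadjusted paired t-test under simple randomisation, simulated over these settings: 4.8 to 5.3%.

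**What each remedy contributes in Study 3.**
- 17:17 with no period term: type I error falls to 2.6 to 4.8%, because visit variance stays in the error term, and power does not improve (34% against 35% at ρ = 0.5, π = 0.4, for an illustrative 0.3 SD effect).
- Period term with a 22:12 split: the SE is √[(1/22 + 1/12)/(4/34)] = 1.046 times that at 17:17.
- Period term and 17:17, against simple randomisation with an unadjusted test, for a 0.3 SD effect: power rises from 38% to 40% at ρ = 0.5, π = 0.2, and from 49% to 59% at ρ = 0.7, π = 0.4.

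In Study 2, with participant and period fitted, random order costs about 4% in contrast variance against exact balance.

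**Does balance fit the planned numbers?** A Williams design for five treatments has 10 sequences, and 30/10 = 3 people per sequence. Each dose then falls 6 times at each visit, and each ordered pair of doses is adjacent 6 times. In Study 3, 34 = 17 + 17 in each cohort.

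**The case against.** The strongest reply is that the documents do not describe an unbalanced list. A Williams list or a blocked two-sequence list could sit in the sealed envelopes without contradicting any sentence. Nor does the ANOVA wording exclude participant and period as factors. This stands: the fault is under-specification, and every probability above depends on simple randomisation.

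A reader might infer that the dose and treatment estimates are biased, or that false positives rise. Neither follows. Under random order the leakage averages zero, and simulated type I error stays near 5%. What remains is extra variance, and a shift of unknown sign in the one list actually drawn.

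A reader might also infer unbalanced carry-over between doses. The documents do not support that concern: each visit uses a single dose, visits are at least a week apart, and Study 1 expects to follow elimination over three half-lives within an 8-hour visit.

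Finally, once period is in the model, exact balance adds only a few per cent. That is correct, and it is why the model is the main change. It does not remove the case for balance, which needs no extra visits or participants and cannot be restored once the envelopes are used.

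**Conclusion.** The point holds as a gap in specification with a modest cost in precision. Neither the sequences nor a period term is stated for two crossover studies whose planned numbers allow exact balance. For Study 3, assumed period effects of 0.2 to 0.4 SD and within-person correlations of 0.5 to 0.7 put the increase in the SD of the unadjusted estimate at about 2 to 13%. For Study 2, an assumed drift of 0.1 SD per visit gives typical leakage of about 0.04 SD in a dose contrast. That is small against the planned effect, but could matter when neighbouring doses are close and one must be chosen. If there is no visit effect, or the envelopes are already balanced and period is fitted, the loss disappears. The change should be made, but the trial does not stand or fall on it.

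**What to change.** 1. **Analysis (the main gain).** State in Section 7, before data collection, that both studies use a within-participant model with participant, period and dose or treatment. It remains valid if dropout breaks the balance, which matters because the plan replaces only screen failures. Cost in error degrees of freedom against a participant-plus-treatment model: Study 2 goes from 116 to 112 (150 observations, less 1, 29 and 4, then less 4 for period); Study 3 goes from 33 to 32 per cohort.
2. **Randomisation.** State in Section 3 that the Study 2 envelopes are filled from a 10-sequence Williams design with each sequence used three times, and that in Study 3 each cohort has 17 propionate-first and 17 placebo-first participants, assigned in random order.

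The remaining cost is preparing the list before the envelopes are filled and a few sentences of protocol text. No extra visits or participants are needed.

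### The 80% and 90% power figures are two-independent-groups figures for within-person comparisons, and the printed AIRg SD of 48.7 does not fit a 40% rise being 0.79 SD

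*Combined protocol and SAP*

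**What the plan says.** All quotes are from section 3 (Study Design) of the combined protocol and SAP.

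- **Study 2, sample size.** The expected effect is 0.73 SD of the insulinogenic index (mean 0.99, SD 0.85). "This can be detected as significant at p<0.05, with 80% power using 30 in each group. Screen failures will be replaced".
- **Study 2, design.** Thirty people are enrolled. "Each participant will receive all doses of propionate", and the levels are listed in "They will randomly be assigned an oral dose of propionate, either 0, 1, 3, 6, 9g". The outcome feeds Study 3, which uses "oral administration of propionate at the most effective dose determined in study 2".
- **Study 3, sample size.** The reference values are given as "Mean IVGTT-AIRg in a group of 306 healthy subjects was 492 mU.min (SD 48.7"; their source is unpublished. After log transformation, "it was estimated that a 40% increase in IVGTT-AIRg would constitute an increase of 0.79 SD". The 40% comes from propionate-treated against saline-treated mice. The power claimed for this effect reads "which could be detected as significant at p<0.05, with 90% power using 34 in each group".
- **Study 3, design.** Two cohorts of 34 each take part in a "randomised double blind placebo controlled crossover study".
- **Section 7.** It names t-tests for two groups and ANOVA for three or more, and says the methods can be confirmed only when data collection is complete. It does not mention a paired, crossover or repeated-measures form.
- **Section 1.** The aims include the effect of diabetes risk on beta cell function, which is a comparison between the two Study 3 cohorts.

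**The concern.** Both sample-size paragraphs express the effect in SDs taken from samples of different people and count participants per group. Neither study has two independent treatment groups. In both, propionate is compared with 0 g or placebo in the same person, so the relevant spread is that of the within-person difference. The documents give neither that SD nor a correlation from which to derive it.

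The Study 3 paragraph has a second problem. The printed mean and SD imply a coefficient of variation of about 10%. With so little spread, a 40% rise should be several SDs, not less than one.

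At stake is whether a reader can tell what power the studies have, for which comparison, and under which analysis, and whether the effect size that fixes 34 per cohort can be traced to its inputs.

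**Working it through.** **1. Reproduce the stated power.** Inputs from section 3: d = 0.73 with n = 30, d = 0.79 with n = 34, and α = 0.05 (sidedness not stated). For two independent groups the noncentrality is d√(n/2).

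- Study 2: 0.73 × √15 = 2.827. Power is 80.7% by normal approximation and 79.4% by t (58 df).
- Study 3: 0.79 × √17 = 3.257. Power is 90.3% by normal approximation and 89.4% by t (66 df).

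Both match at two-sided 5%. One-sided tests do not (87.5% and 94.3%). Nor does reading 0.73 and 0.79 as SDs of a paired difference (97.1% and 99.4%). A paired calculation with a correlation near 0.05 would also land on 80% and 90%, but the text states no correlation and counts participants per group.

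**2. Power on the actual design.** With equal SDs under both treatments and within-person correlation ρ, the SD of the difference is SD × √(2(1−ρ)). The paired effect is therefore d_z = d/√(2(1−ρ)), tested on n−1 df. The documents give no ρ, so the values below are assumed. Figures are for one comparison, complete data and two-sided 5%.

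| ρ (assumed) | Study 2 d_z | Study 2 power | Study 3 d_z | Study 3 power (per cohort) |
|---|---|---|---|---|
| 0 | 0.516 | 78.0% | 0.559 | 88.5% |
| 0.3 | 0.617 | 90.4% | 0.668 | 96.5% |
| 0.5 | 0.730 | 97.1% | 0.790 | 99.4% |

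At ρ = 0 the noncentrality equals that of step 1; power is slightly lower only because the degrees of freedom are halved. Paired power reaches the stated 80% and 90% at ρ of about 0.05 in each study.

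Without assuming ρ, the detectable effects are:

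- 30 people, 80% power: d_z = 0.53.
- 34 people, 90% power: d_z = 0.57.

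**3. Does the 90% cover cohort against cohort?** No. The 40% effect is propionate against saline, which is the within-person contrast. A comparison of within-person differences between cohorts is a two-sample test, 34 against 34. It has 80% power for 0.69 SD of the difference.

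**4. AIRg inputs.** Mean 492, SD 48.7, rise 40%.

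- Raw scale: 0.40 × 492 = 196.8, and 196.8/48.7 = 4.04 SD.
- Log scale (log-normal assumed): CV = 48.7/492 = 0.099, log-SD = √ln(1 + 0.099²) = 0.0987, and ln 1.4/0.0987 = 0.3365/0.0987 = 3.41 SD.

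Working back from 0.79 SD, the log-SD is 0.3365/0.79 = 0.426, a CV of √(exp(0.426²) − 1) = 0.446. The raw SD this implies depends on what 492 is:

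- an arithmetic mean of log-normal data: 492 × 0.446 = 219;
- a geometric mean: about 240;
- no log transformation at all: 196.8/0.79 = 249.

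Other readings of 48.7 also miss 0.79:

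- a standard error (SD = 48.7 × √306 = 852): 0.29 SD log, 0.23 raw;
- a misprint for 487: 0.41 log, 0.40 raw;
- a CV of 48.7%: 0.73 log, 0.82 raw, which is close but not exact.

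**The case against.** The strongest reply is that nothing is miscalculated: 0.73 SD with 30 and 0.79 SD with 34 do give about 80% and 90%. Without a within-person SD, a between-person SD is a cautious stand-in, since repeat tests in one person would ordinarily correlate positively. This stands, and it is why the point cannot be called a shortfall. It does not make the statement correct for the design, and the plan does not say that the figure is meant as a cautious stand-in.

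A second reply is that the group in the Study 3 statement means cohort. Each cohort does have 34, but the effect being powered is propionate against control, and the 90% is obtained by placing 34 people on each side of that contrast.

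A third is that t-tests and ANOVA include paired and repeated-measures forms. That is fair. A reader might infer that section 7 prescribes an unpaired analysis; it does not. It leaves the form open.

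On AIRg, 0.79 SD is attributed to log-transformed unpublished data, and 34 does not use 48.7. Both are true, so the step from 0.79 to 34 is intact. The log transformation alone does not close a gap of more than fourfold between 0.79 and 3.41.

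**Conclusion.** The point holds as a wrong power basis and an inconsistent design input. The stated 80% and 90% belong to a two-independent-groups design. For a single within-person comparison with complete data they are conservative once the correlation passes about 0.05; at zero correlation, power is 78.0% and 88.5%. These figures assume equal SDs under both treatments, a two-sided 5% test and the correlations shown, none of which the documents give. The printed SD of 48.7 is wrong or unexplained: 0.79 SD requires a log-SD of about 0.426, or a raw SD of roughly 219 to 249.

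Four stronger readings are tempting but not supported:

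- **The studies are underpowered.** Any clearly positive correlation gives more than the stated power for the single comparison.
- **Study 2 falls short across its four doses.** That result depends on a multiplicity rule chosen by the reader. The plan states none, and it describes an open-label dose-finding study without a confirmatory claim for each dose.
- **Withdrawals will not be replaced.** The plan says that screen failures are replaced and is silent on withdrawals.
- **The cohort comparison has a specific low power.** The plan gives no expected difference between cohorts, so only a detectable difference can be stated.

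**What to change.** **(a) Sample-size paragraphs, section 3.** Restate on the paired basis, for example:

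> Study 2: thirty people with complete data on 0 g and a given dose provide 80% power (paired test, two-sided 5%, one dose against 0 g, unadjusted) for a mean difference of 0.53 SD of the within-person difference. At an assumed within-person correlation of [r], the expected 0.73 SD equals [x] SD of that difference.

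> Study 3: thirty-four people with complete data in a cohort provide 90% power (paired test, two-sided 5%) for a mean difference in log AIRg of 0.57 SD of the within-person difference in that cohort. At an assumed within-person correlation of [r], the expected 0.79 SD equals [x] SD of that difference.

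**(b) Section 7.** Name the analyses.

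- Study 2: repeated-measures ANOVA, or a mixed model with dose and visit as fixed effects and participant as a random effect.
- Study 3: paired or crossover analysis of log AIRg within each cohort.
- Diabetes-risk aim: an independent-samples comparison of within-person differences between cohorts. Note that the 90% does not apply to it and that 34 against 34 gives 80% power for 0.69 SD of the difference.

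A multiplicity rule for the four doses is optional.

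**(c) Study 3 inputs.** Correct or explain the SD of 48.7 and print the log-scale SD that produced 0.79.

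The cost is rewording of two paragraphs and section 7, with no added visits or blood sampling. Enrolment changes only if the authors choose to power the cohort comparison.
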